### 11.3. Exploratory Pharmacodynamic and Biomarker Analyses

#### 11.3.1. Endpoint / Variables

Exploratory Objectives	Exploratory Endpoints

 
To investigate the effect of daprodustat and epoetin alfa on vasoactive mediators of blood pressure
 
	
 
Plasma concentrations and derived parameters including Cmax, tmax, and AUC(0-24) as appropriate (to include erythropoietin, endothelin-1, nitric oxide, asymmetric dimethylarginine, renin, angiotensin-II and metabolites, and noradrenalin)
 

CONFIDENTIAL

205665

Exploratory Objectives	Exploratory Endpoints

 
To summarize the effect of daprodustat and epoetin alfa on SBP after Acute Challenge 1 and Acute Challenge 2
 
	
 
AUEC of SBP as measured by ABPM over 24-hr post-dosing
 

 
To compare the effect of daprodustat to epoetin alfa on SBP after 8 weeks of Hgb maintenance therapy
 
	
 
Change from Day 1 pre-dose SBP to Day 57 pre-dose
 

 
To compare the effect of daprodustat to epoetin alfa on SBP at Cmax of the study treatment
 
	
 
Change in SBP from pre-dose on Day 1 to Cmax of the study treatment on Day 1, as measured by ABPM
 
Change in SBP from pre-dose on Day 1 to Cmax of the study treatment on Day 57, as measured by ABPM
 
Change in SBP from pre-dose on Day 57 to Cmax of the study treatment on Day 57, as measured by ABPM
 

 
To compare the effect of daprodustat to epoetin alfa on SBP at Cmax of the erythropoietin level
 
	
 
Change in SBP from pre-dose on Day 1 to Cmax of erythropoietin on Day 1, as measured by ABPM
 
Change in SBP from pre-dose on Day 1 to Cmax of erythropoietin on Day 57, as measured by ABPM
 
Change in SBP from pre-dose on Day 57 to Cmax of erythropoietin on Day 57, as measured by ABPM
 

### 11.3.1.1. Statistical Methodology Specification

Endpoint / Variables

 
Cmax, tmax, and AUC(0-24) for erythropoietin, endothelin-1, nitric oxide, asymmetric dimethylarginine, renin, angiotensin-II and metabolites, and noradrenalin
 
AUEC of SBP, comparing Day 57 vs Day 1
 
Change in pre-dose SBP from Day 1 to Day 57
 
Change in SBP from pre-dose on Day 1 to Cmax of the study treatment on Day 1, as measured by ABPM
 
Change in SBP from pre-dose on Day 57 to Cmax of the study treatment on Day 1, as measured by ABPM
 
Change in SBP from pre-dose on Day 57 to Cmax of the study treatment on Day 57, as measured by ABPM
 
Change in SBP from pre-dose on Day 1 to Cmax of erythropoietin on Day 1, as measured by ABPM
 
Change in SBP from pre-dose on Day 57 to Cmax of erythropoietin on Day 1, as measured by ABPM
 
Change in SBP from pre-dose on Day 57 to Cmax of erythropoietin on Day 57, as measured by ABPM
 

Overview of exploratory endpoints

 
For each acute challenge, the concentration of erythropoietin, endothelin-1, nitric oxide, asymmetric dimethylarginine, renin, angiotensin-II and metabolites, and noradrenalin will be summarized by treatment group at each timepoint. Descriptive statistics (n, arithmetic mean, standard deviation, minimum, median, maximum) will be calculated for all biomarkers endpoints by regimen. In addition, for AUC, Cmax, tmax, baseline adjusted AUC and baseline adjusted Cmax; geometric means and geometric CVs (CVb(%)) will be calculated for each regimen. Geometric mean and geometric CV% will not be calculated for tmax. Line graphs of this information will be provided by treatment group for
 

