
 
● Nitrate umol/L = Nitrite Total - Nitrite Endogenous 
 
○ The Nitrate concentration is an indirect method to estimate Nitric Oxide.
 
○ Nitric Oxide label will be used in place of nitrate concentration
 
 
 
● Geometric mean=exp (mean on loge scale)
 
● CVb (%)=SQRT(exp(SD**2)-1)x100, where SD is the standard deviation of the loge-transformed data.
 
● Natural Log-transformation, (Ln), of biomarker data will not be done for Tmax
 
● AUC(baseline corrected) = Calculated AUC - (baseline level*time) 
 
○ Where baseline level is defined as the pre-dose measurement for each visit
 
○ Where time is the last time measurement, for most subjects this would be 24 hours.
 
○ To be done on a by subject level then summarized by treatment for each visit
 
 
 
● Cmax(baseline corrected) = Cmax - baseline level 
 
○ Where baseline level is defined as the pre-dose measurement for each visit
 
○ To be done on a by subject level then summarized by treatment for each visit
 
 
 
	
Parameter	Parameter Description
AUC(0-24)	
Area under the concentration-time curve from time zero to the time of the last quantifiable concentration (C(t)) will be calculated using the linear trapezoidal rule for each incremental trapezoid and the log trapezoidal rule for each decremental trapezoid.
 
 
○ If subject is missing pre-dose or 24-hour data, then exclude from AUC calculation.
 

Cmax	Maximum observed plasma concentration, determined directly from the concentration-time data.

CONFIDENTIAL

205665

Pharmacodynamic and Biomarker					
Tmax	Time to reach Cmax, determined directly from the concentration-time data.				
Exploratory endpoints					

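### Geometric means and ln summaries are specified for baseline-adjusted biomarker AUC and Cmax, which can be zero or negative, with no rule for such values (exploratory display, low impact)

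*SAP*

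**What the plan says.** SAP 11.3.1.1 gives two layers of summary for the exploratory biomarkers. The first is untransformed: "Descriptive statistics (n, arithmetic mean, standard deviation, minimum, median, maximum) will be calculated for all biomarkers endpoints by regimen". The second adds log-scale statistics for a list of parameters that ends with "baseline adjusted AUC and baseline adjusted Cmax; geometric means and geometric CVs (CVb(%)) will be calculated for each regimen".

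SAP 14.6.6 (Biomarker Derivations) defines the adjusted parameters subject by subject, taking the pre-dose sample of the same visit as baseline:

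- Adjusted AUC: "AUC(baseline corrected) = Calculated AUC - (baseline level*time" (closing bracket omitted).
- Adjusted Cmax: "Cmax(baseline corrected) = Cmax - baseline level".

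The same section defines the geometric mean as the exponential of the mean of the natural logs and states a single exemption: "Natural Log-transformation, (Ln), of biomarker data will not be done for Tmax".

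In SAP 14.12.8, Table 4.34 (non-transformed) and Table 4.35 (ln-transformed) carry the same programming note, which asks for both adjusted parameters.

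**The concern.** A geometric mean exists only for positive values. A difference from pre-dose is positive only when the marker goes up. The SAP therefore asks for a statistic that fails for any subject whose time-averaged level is at or below pre-dose, and leaves the response to the programmer.

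The likely default is that such values become missing. The ln summary would then cover only subjects whose marker rose and could never show a fall. Because retention depends on the response, the retained subsets of the two arms need not be comparable. The objective is to investigate the effect of each drug on vasoactive mediators, so direction of change is what a reader would look for. Other devices, such as adding a constant or taking absolute values, would be chosen after the data are seen.

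**Working it through.** The plan gives no figure to reproduce here. The check is algebraic, followed by an illustration of frequency.

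**Worked example.** This uses the SAP's linear-up/log-down rule and the sampling times in SAP Appendix 2 (pre-dose, then 1, 2, 4, 6, 8 and 24 h). The values are hypothetical: 10, then 9, 8.5, 9, 9.5, 9, 9.8.

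| Interval (h) | Rule | Area |
|---|---|---|
| 0-1 | (10 - 9)/ln(10/9) | 9.49 |
| 1-2 | (9 - 8.5)/ln(9/8.5) | 8.75 |
| 2-4 | 2 x (8.5 + 9)/2 | 17.50 |
| 4-6 | 2 x (9 + 9.5)/2 | 18.50 |
| 6-8 | 2 x (9.5 - 9)/ln(9.5/9) | 18.50 |
| 8-24 | 16 x (9 + 9.8)/2 | 150.40 |
| Total | | 223.1 |

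Adjusted AUC = 223.1 - 10 x 24 = -16.9, so the log is undefined. Adjusted Cmax = 10 - 10 = 0 if pre-dose counts towards Cmax, or 9.8 - 10 = -0.2 if only post-dose samples count. The SAP does not say which applies; both fail on the log scale.

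**Rules that might have covered it.** None does:

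- SAP 14.6.6 excludes subjects missing a pre-dose or 24-hour sample from AUC.
- SAP 14.5.3 imputes pharmacokinetic concentrations.
- SAP 14.6.4 handles non-detectable safety laboratory values.
- SAP 14.7.2 only requires exclusions to be documented.

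**How often.** Every input here is assumed: log-normal marker, independent samples, the schedule above, and a constant post-dose shift.

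| Within-subject CV | Post-dose shift | Adjusted AUC <=0 | Adjusted Cmax <=0 |
|---|---|---|---|
| 10% | none | 49.6% | 14.1% |
| 10% | +10% | 19.0% | 2.8% |
| 10% | +25% | 2.2% | 0.2% |
| 20% | none | 48.4% | 14.4% |
| 20% | +10% | 32.1% | 6.9% |
| 20% | +25% | 14.7% | 2.1% |
| 30% | none | 47.8% | 14.6% |
| 30% | +10% | 35.4% | 8.7% |
| 30% | +25% | 23.3% | 4.6% |

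The no-change Cmax figures can be checked by hand: with seven exchangeable samples, pre-dose is the largest with probability 1/7 = 14.3%.

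With 25 subjects per arm (SAP 14.7.1), the chance of at least one adjusted AUC <=0 is 1 - (1 - p)^25. For the smallest p, 0.022, this is 43%; for p = 0.190 it is over 99%.

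**Effect of dropping the values.** Assumed: a 10% fall held from the first post-dose sample to 24 h, within-subject log-SD 0.1-0.3, between-subject log-SD 0.4, and adjacent-sample correlation 0 or 0.5. Ranges also run over sampling schedules. Adjusted AUC is <=0 in 59-83% of subjects. The geometric mean of the rest is +3 to +15% of baseline AUC, against an arithmetic mean over all subjects of about -10 to -11%. If the fall lasts 8 h and is gone by 24 h, the figures are 55-73%, +4 to +17%, and -6 to -7%.

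Large rises nearly remove the problem. With a sustained threefold rise, at most 0.1% of adjusted AUCs are <=0; if the rise lasts 4 h and is gone by 8 h, at most 12%.

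**The case against.** The algebra is not in dispute. The case for leaving the plan alone has four parts.

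*A rule may exist elsewhere.* Tables 4.34 and 4.35 use the sponsor's standard shell PK06, and SAP 14.5.2 applies the sponsor's reporting library unless otherwise stated. That library was not available for checking and could hold a convention. This stands as a limit on the claim: the SAP text states no rule and cites none for this case.

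*The effect is trivial.* The adjusted parameters are extra descriptive rows, not listed endpoints, and the smaller n would be visible beside Table 4.34. This is right, and the point is rated accordingly.

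*Deletion is too broad.* Erythropoietin is expected to rise in both arms, so its log-scale summary would be largely computable. A line restricting ln statistics to positive values, with the number <=0 shown, would be enough. The first part is fair. The restriction, however, is the selection that prevents the table from showing a fall, and erythropoietin keeps geometric summaries of its unadjusted AUC and Cmax.

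*The magnitudes are assumed.* They are. The ranges for the 10% fall also pool the SAP schedule with the one that Protocol Table 4 appears to show (0.5, 1, 3, 4, 6, 24 h), which may be a column shift from text extraction. That widens some ranges, mainly for short-lived shifts. The defect depends on none of these figures.

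**Conclusion.** The concern holds. Two quantities defined as differences are assigned statistics that require positive values, in the methods text and again in a table specification, with no stated handling when the condition fails. For a marker that changes little, under the assumptions above, about half of the adjusted AUCs and roughly one in seven adjusted Cmax values (seven-sample markers) would have no logarithm. For a marker that rises strongly and stays up, almost none would be lost.

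The consequence is confined to one exploratory descriptive table. The conclusion that no rule exists covers the SAP text only, not the sponsor's external reporting standards.

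**What to change.** 1. In SAP 11.3.1.1, remove baseline-adjusted AUC and Cmax from the geometric mean and CV sentence. That sentence needs editing anyway, because it lists tmax and the next sentence withdraws it.
2. In SAP 14.12.8, remove both from the Table 4.35 programming note. Keep them in Table 4.34 with n, arithmetic mean, SD, median and range.
3. In SAP 14.6.6, extend the Tmax exemption from ln-transformation to both adjusted parameters.

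These are wording edits and a table note; no new data are needed. Subjects missing pre-dose or 24-hour data stay excluded from AUC as now.

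Optional, only if a log-scale summary relative to baseline is wanted: report the geometric mean of AUC(0-t)/(pre-dose x t), following the ratio-to-baseline method in SAP 5.2.2. Here t must be the end of that subject's own AUC. SAP 14.6.6 runs the AUC to the last quantifiable sample, but for the baseline subtraction says "Where time is the last time measurement, for most subjects this would be 24 hours". A flat marker whose AUC stops at 8 h has a ratio of about 1 with t = 8, but 8/24 = 0.33 with a fixed 24 h. Show how many ratios cannot be formed, including for nitric oxide, which is itself a difference ("Nitrate umol/L = Nitrite Total - Nitrite Endogenous") and may be <=0. Footnote that a Cmax/pre-dose ratio cannot fall below 1 if pre-dose counts towards Cmax. This option needs a small programming change.

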**CONFIDENTIAL**

205665

each acute challenge. Cmax, tmax, AUC(0-24), baseline adjusted AUC and baseline adjusted Cmax will all be summarized by treatment arm and for each acute challenge day.
 
 
• Change in AUEC of SBP from Day 57 to Day 1 for each treatment arm will be summarized in a table.
 
• The difference in SBP between pre-dose in Acute Challenge 1 and pre-dose in Acute Challenge 2 will be summarized by treatment group. Similar summaries of DBP, MAP, and HR will be performed.
 
• For each acute challenge, change from pre-challenge in SBP, DBP, MAP, and HR will be summarized by treatment group at each timepoint. In addition, for each acute challenge, SBP, DBP, MAP, and HR will be summarized by treatment group at each timepoint. Line graphs of this information will be provided by treatment group for each acute challenge.
 
• For the following endpoints, an ANCOVA model will be used with terms for baseline SBP, treatment, and prior ESA dose (low/high): 
 
○ Change in SBP from pre-dose on Day 1 to Cmax of the study treatment on Day 1, as measured by ABPM
 
○ Change in SBP from pre-dose on Day 57 to Cmax of the study treatment on Day 1, as measured by ABPM
 
○ Change in SBP from pre-dose on Day 57 to Cmax of the study treatment on Day 57, as measured by ABPM
 
○ Change in SBP from pre-dose on Day 1 to Cmax of erythropoietin on Day 1, as measured by ABPM
 
○ Change in SBP from pre-dose on Day 57 to Cmax of erythropoietin on Day 1, as measured by ABPM
 
○ Change in SBP from pre-dose on Day 57 to Cmax of erythropoietin on Day 57, as measured by ABPM
 
 
 

Model Checking & Diagnostics
 
 
• Distributional assumptions underlying the statistical analyses will be assessed by visual inspection of residual plots. Normality will be examined by normal probability plots, while homogeneity of variance will be assessed by plotting the residuals against the predicted values for the model. If assumptions are grossly violated, alternative analyses will be considered.
 


Presentation of Exploratory Endpoints
 
 
• Line graphs for each acute challenge and each biomarker by treatment group
 
• Table summaries for AUEC of SBP, comparing Day 57 vs Day 1, and change in pre-dose SBP from Day 1 to Day 57
 
• Plot of hourly average ABPM will be created for SBP, over-lay for both AC1 and AC2.
 
• The point estimate, two-sided 95% CI and p-value for the difference between treatment groups will be presented from all ANCOVA models.
 

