**CONFIDENTIAL**

205665

Challenge 1 and 2) interaction. Note that the pre-challenge ABPM (DBP/MAP/HR) may change over time between Acute Challenge 1 and Acute Challenge 2 as a result of the maintenance therapy, and thus the pre-challenge ABPM (DBP/MAP/HR) at Acute Challenge 2 is not a true pre-treatment covariate. As a result, the interpretation of the effect of the Acute Challenge 2 may be confounded by the impact of treatment phase on the covariate. Therefore, if the interaction term in this model is significant at the 0.10 level, then the primary model will be ANCOVA with terms for treatment, prior ESA dose (low/high), and post-HD/pre-Acute Challenge 1 ABPM (DBP/MAP/HR).
 
 
For the second secondary endpoint, AUEC of SBP, DBP, HR, and MAP post-acute challenge 1 and 2 will be analyzed using an ANCOVA model with terms for treatment and prior ESA dose (low/high).
 
The AUEC for ABPM will only be analysed if a subject has ABPM data up to hour 24. 
 
For example if the subject has ABPM data up to hour 23, the subject will be excluded from the ABPM AUEC analysis.
 
If more than 25% of subjects are excluded from the ABPM AUEC analysis because the subject is missing any of the 3 possible hour 24 ABPM measurements, then an extrapolation technique of average hour 23 measurement carried forward to hour 24 may be utilized as a sensitivity analysis for AUEC ABPM.
 
 
 

Model Checking & Diagnostics
 
 
Distributional assumptions underlying the statistical analyses will be assessed by visual inspection of residual plots. Normality will be examined by normal probability plots, while homogeneity of variance will be assessed by plotting the residuals against the predicted values for the model. If assumptions are grossly violated, alternative analyses will be considered.
 
Section 14.6.6 outlines any transformation of data as needed.
 

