**CONFIDENTIAL**

205665

Pharmacodynamic and Biomarker: Tables					
No.	Population	IDSL / Example Shell	Title	Programming Notes	Deliverable
4.18.	ITT	PDT4	Summary of Analysis of AUEC DBP over 24hr post-AC2		DR, SAC
4.19.	ITT	PDT4	Summary of Analysis of AUEC MAP over 24hr post-AC2		DR, SAC
4.20.	ITT	PDT4	Summary of Analysis of AUEC HR over 24hr post-AC2		DR, SAC
4.21.	ITT	PDT5	Summary of change from pre-dose SBP	At each timepoint on day 1 and day 57 by treatment	DR, SAC
4.22.	ITT	PDT5	Summary of change from pre-dose DBP	At each timepoint on day 1 and day 57 by treatment	DR, SAC
4.23.	ITT	PDT5	Summary of change from pre-dose MAP	At each timepoint on day 1 and day 57 by treatment	DR, SAC
4.24.	ITT	PDT5	Summary of change from pre-dose HR	At each timepoint on day 1 and day 57 by treatment	DR, SAC
Exploratory Endpoints					
4.25.	ITT	PDT6	Summary of Change from Day 1 AUEC of 24hr SBP to Day 57 AUEC of 24hr SBP		DR, SAC
4.26.	ITT	PDT7	Summary of change from Day 1 pre-dose SBP to Day 57 pre-dose		DR, SAC
4.27.	ITT	PDT3	Summary of Analysis of change in SBP from pre-dose on Day 1 to Cmax of the study treatment on Day 1, as measured by ABPM		DR, SAC
4.28.	ITT	PDT3	Summary of Analysis of change in SBP from pre-dose on Day 57 to Cmax of the study treatment on Day 1, as measured by ABPM		DR, SAC
4.29.	ITT	PDT3	Summary of Analysis of change in SBP from pre-dose on Day 57 to Cmax of the study treatment on Day 57, as measured by ABPM		DR, SAC

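### The exploratory objective to compare the arms on pre-dose SBP after 8 weeks of maintenance has only a by-arm summary, so no modelled between-arm estimate or CI is planned for the maintenance effect in isolation

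*SAP*

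**What the plan says.** Protocol Section 3 and SAP 2.2 and 11.3.1 state the objective as "To compare the effect of daprodustat to epoetin alfa on SBP after 8 weeks of Hgb maintenance therapy", with the endpoint "Change from Day 1 pre-dose SBP to Day 57 pre-dose". In the same table, the objective for 24-hour AUEC of SBP is worded as *summarize*, and the two objectives for SBP at Cmax are worded as *compare*.

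For the pre-dose change, SAP 11.3.1.1 says: "The difference in SBP between pre-dose in Acute Challenge 1 and pre-dose in Acute Challenge 2 will be summarized by treatment group". Protocol 9.4.3 says the same. The presentation part of SAP 11.3.1.1 lists "Table summaries for AUEC of SBP, comparing Day 57 vs Day 1, and change in pre-dose SBP from Day 1 to Day 57". It then says "The point estimate, two-sided 95% CI and p-value for the difference between treatment groups will be presented from all ANCOVA models". The exploratory ANCOVA list names six SBP-at-Cmax endpoints, with terms for baseline SBP, treatment and prior ESA dose. The pre-dose change is not on it.

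The display list in SAP 14.12.8 follows suit. Table 4.26 is "Summary of change from Day 1 pre-dose SBP to Day 57 pre-dose" on shell PDT7. Tables 4.27 to 4.32, for the Cmax endpoints, are titled as analyses and use shell PDT3.

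**The concern.** The verb and the method do not match. The objective worded as *summarize* gets a summary, and two of the three worded as *compare* get a model with an estimate, 95% CI and p-value. The third, on pre-dose SBP, gets by-arm summaries only.

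The omission touches the trial's rationale. Protocol 2.1 cites an average SBP rise of about 5 to 8 mmHg on ESA therapy. Protocol 4.4 chose 8 weeks because the hypertensive effect has been seen at 4 to 8 weeks. The pre-dose change is the planned endpoint that looks at this period without an acute dose on top. Two by-arm means, with no interval on their difference, can be read too easily as showing a difference or as showing none. A comparative objective without a specified comparison also invites a post hoc test.

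**Working it through.** **1. The plan's own figure.** Protocol 9.2.1 gives no figure for this endpoint. For the primary endpoint it assumes SD 16 mmHg, 25 per arm and two-sided 5%. Half-width = t(0.975, 48) × SD × √(2/25) = 2.0106 × 16 × 0.2828 = 9.1 mmHg, as stated. Power for 15 mmHg by noncentral t is 90.1%, against 90% in Table 6. Both reproduce.

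**2. Does another planned output isolate the maintenance effect?**
- *Initial primary model* (SAP 11.1.5.2): it includes the change in pre-challenge SBP between the two challenges, which the SAP itself says maintenance may alter. That part of the effect is adjusted away.
- *Fallback primary model*: it omits that change, but is used only if the interaction is significant at 0.10. Its outcome is measured after the acute dose.
- *Day 57 AUEC* (SAP 11.2.5.1): "AUEC of SBP, DBP, HR, and MAP post-acute challenge 1 and 2 will be analyzed using an ANCOVA model with terms for treatment". The only other term is the stratification factor. This model always runs and reports a CI, but is also post-dose and has no baseline SBP term.
- *Cmax endpoints*: each uses a post-dose reading.

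An illustrative simulation shows the consequence. Assumptions: 25 per arm, SD 16, Day 1/Day 57 pre-dose correlation 0.5, coefficient 0.7 of the post-dose average on Day 57 pre-dose SBP, maintenance effect carried fully into the post-dose average, 4,000 runs. The treatment-plus-ESA-dose column stands in for the AUEC model. Entries are mean treatment estimates in mmHg; the initial primary model is read at the mean change.

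| True maintenance | True acute | Initial primary | Fallback | Treatment + ESA dose | Pre-dose change ANCOVA |
|---|---|---|---|---|---|
| −8 | 0 | −2.4 | −8.0 | −8.0 | −7.9 |
| −8 | −7 | −9.4 | −15.0 | −15.1 | −8.1 |
| 0 | −8 | −8.0 | −8.1 | −8.1 | −0.1 |

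The initial primary column follows by hand: (1 − 0.7) × (−8) + 0 = −2.4 and (1 − 0.7) × (−8) − 7 = −9.4. The fallback and treatment-plus-ESA models return the sum of the two effects. Only the ANCOVA of pre-dose change returns the maintenance effect in all three rows.

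**3. Precision of the missing comparison.** The documents give no SD for pre-dose SBP. Assumed: subject SD 12-14, visit SD 6-8, reading SD 9-12 mmHg, 25 per arm. Let S be the subject variance, e the visit plus reading variance, T = S + e and r = S/T.
- Low end: S = 144, e = 36 + 81 = 117, T = 261, r = 0.552. ANCOVA residual SD = √[T(1 − r²)] = 13.5; half-width = t(0.975, 46) × 13.5 × √(2/25) = 2.0129 × 13.5 × 0.2828 = 7.7. Raw-change SD = √(2e) = 15.3; half-width = 2.0106 × 15.3 × 0.2828 = 8.7.
- High end: S = 196, e = 64 + 144 = 208, T = 404, r = 0.485. ANCOVA residual SD = 17.6, half-width 10.0. Raw-change SD = 20.4, half-width 11.6.

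A second parameterisation uses the protocol's SD range of 14-20 with an assumed correlation of 0.3-0.7. ANCOVA half-widths are then 5.7-10.9 mmHg and raw-change half-widths 6.2-13.5. At SD 16 and r = 0.5 they are 7.9 and 9.1, with ANCOVA power of about 24% for 5 mmHg and 52% for 8 mmHg.

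**The case against.** A reader might infer that the trial will give no estimate or interval at all for the maintenance effect on blood pressure, and that the objective cannot be answered. The documents do not support that. The Day 57 AUEC ANCOVA always reports a between-arm difference with a 95% CI, and the fallback primary model does so when it is triggered. Both include the maintenance effect, though mixed with the acute dose. Table 4.26 also gives the change by arm, so a crude difference follows by subtraction, and an unadjusted interval too if n and SD are shown. The PDT7 shell is in a separate document, so its columns could not be checked.

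The endpoint is also imperfect. Participants were on an ESA until the washout, so Day 1 is not an ESA-naive baseline. Protocol 6.11.1 keeps participants in the study when antihypertensive treatment changes. Under SAP 14.6.6 the pre-dose value is a single time-zero ABPM reading, or a post-dialysis vital-signs value if that is unavailable. A descriptive summary of a noisy exploratory measure is a defensible choice. These points limit interpretation, but noise favours an interval and baseline adjustment over bare means.

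Finally, the objective is exploratory, SAP 5.5 makes no Type I error adjustment for such analyses, and protocol and SAP agree with each other. All of that stands and limits the weight of the point. It does not supply the missing comparison.

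**Conclusion.** The concern holds in a limited form. The objective is comparative, its endpoint has only a by-arm summary, and no modelled between-arm estimate or CI is planned for the maintenance effect in isolation. That rests on the text alone. The statement that other planned models mix or adjust away the effect rests on their stated terms and outcomes; the simulation only illustrates it.

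No primary or secondary conclusion changes. The comparison would be an estimate with an interval: a half-width of about 7.7-10.0 mmHg with ANCOVA, against 8.7-11.6 mmHg for raw change, under the assumed variance components. That is about as wide as, or wider than, the 5 to 8 mmHg rise the protocol cites.

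It may be tempting to ask for the same model for DBP, MAP and HR. The documents state no comparative objective for the pre-dose change in those measures and plan only summaries, so the point does not extend to them.

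**What to change.** In SAP 11.3.1.1, add the change in pre-dose SBP from Day 1 to Day 57 to the existing exploratory ANCOVA list. Name the terms as Day 1 pre-dose SBP, treatment and prior ESA dose (low/high), so that the baseline day is unambiguous. Report the treatment difference, two-sided 95% CI and nominal p-value on shell PDT3, labelled exploratory, and keep Table 4.26 as the by-arm summary.

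The cost is a short SAP edit and one display on an existing shell, using data already collected. The downside is one more unadjusted exploratory p-value. Rewording the objective as *summarize* would also remove the mismatch, but the objective stands in Protocol Section 3 as well, and the maintenance effect would still have no modelled estimate of its own.
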